Cover: Statistical Analysis Plan

NCT #: NCT02332915

Title: Effect of Intensity of Treatment on Rehabilitation of Acquired Apraxia of Speech

Date: October 3, 2020

Statistical Analyses

Effect Sizes

Sets of effect size values (d-values) were calculated for each participant as an indication of magnitude of change for *treated items* and *untreated items*: 1) pre-treatment/baseline vs. 2-week follow-up – Intense Phase Items and pre-treatment vs. 2-week follow-up – Traditional (non-intense) Phase Items.

For the pre-treatment versus follow-up comparisons, the three baseline probes immediately preceding application of treatment were used along with the probe completed at two weeks post-treatment. The d-values were derived using the following equation: $ES = (M_{A2} - M_{A1}) / SD_{A1}$. In this equation, “A1” indicates the baseline values and “A2” indicates the 2 week follow up value.

The experimental design was a cross-over design in which each participant received each intensity of treatment in separate, sequential phases (i.e., each participant received two phases of treatment). The arms of the design are designated as Intense First and Traditional First. The arms reflect counterbalancing of order of treatment administration. Order of treatment was not an analysis of interest; there is no evidence to suggest that treatment order would be a pertinent factor in treatment response. The comparison of interest was treatment intensity – Intense versus Traditional treatment phases. Consequently, the data from the Intense phase of treatment for all 24 participants was analyzed relative to the data from the Traditional phase of treatment for all 24 participants.

Descriptive statistics are shown in Tables 1 and 2. Relative to SPT benchmark effect sizes described by Bailey, Eatchel, and Wambaugh (2015) large effect sizes were found for baseline to treatment phase comparisons for treated items for the group for both SPT- Traditional and SPT – Intense, with average effect sizes of 28.9 and 19.7, respectively. For untreated items, large effect sizes

were found for both SPT-Traditional (d=8.1) and SPT-Intense (d=7.9) in for the group. As reflected by the minimum and maximum values in Tables 1 and 2, there were wide ranges of effect sizes found across the individuals.

Table 1

*Effect Size (Δ -values) Descriptive Statistics for **Treated Items** by Treatment Condition for the Group of 24 Participants*

Condition	Comparison	Mean	SD	Minimum	Maximum
d-values					
Intense	BL vs 2 week FU	19.7	12.6	5.2	49.1
Traditional	BL vs 2 week FU	28.9	17.2	6.5	53.1

BL = baseline; Tx = treatment; wk = week

Bailey et al. (2015) benchmarks: small = 5.90, medium, = 7.12, large = 10.19 for baseline to follow-up phase comparisons

Table 2

*Effect Size (Δ -values) Descriptive Statistics for **Treated Items** by Treatment Condition for the Group of 24 Participants*

Condition	Comparison	Mean	SD	Minimum	Maximum
d-values					
Intense	BL vs 2 week FU	7.9	5.6	-4.1	34.6

Traditional	BL vs 2 week FU	8.1	8.9	-1.0	20.9
--------------------	-----------------	-----	-----	------	------

BL = baseline; Tx = treatment; wk = week

Bailey et al. (2015) benchmarks: small = 2.59, medium, = 4.23, large = 6.47 for baseline to follow-up phase comparisons

Comparisons of average group effect sizes were completed using parametric statistics (i.e., dependent *t*-tests, two-tailed) when possible and the nonparametric analogs when normality tests were failed (i.e., Wilcoxon Signed Rank test). For the *treated items*, results of a dependent *t*-test revealed that there was a statistically significant difference between treatment intensity conditions, with $t(23) = 2.698$, p (two-tailed) = .0128. For the untreated items, results of a dependent *t*-test revealed that there was not a statistically significant difference between treatment intensity conditions, with $t(23) = .0735$, p (two-tailed) = .942. The sample mean of treatment TRAD These tests indicate that for the *treated items*, the 2 week follow-up effect size sample mean for Traditional intensity treatment exceeded that for the Intense treatment. Conversely, for the *untreated items*, the 2 week follow-up effect size sample means did not differ by an amount great enough to exclude the possibility that any difference was due to random sampling variability.

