Accuracy of articulation of two sets of experimental words (see “Experimental Stimuli”) was measured repeatedly prior to treatment (see “Probes” for additional detail). For each participant, treatment (SPT-Traditional [SPT-T] or SPT- Intense [SPT-I]) was then applied to one set of experimental words while probing continued with both experimental sets. A two week, no-treatment interval followed the first treatment phase and a two-week maintenance probe was completed at the end of the interval. Repeated probing of the set of items to be treated in the second treatment phase during the no treatment interval (as part of the SCED) ensured that performance was stable prior to the application of treatment with that set. Then, the alternate treatment was applied to the remaining set of items. Follow-up probes were conducted at 2 and 8 weeks following the second treatment phase.

Treatment Order and Experimental Set Assignment. Quasi-randomized assignment was combined with participant matching to assign participants to one of two treatment orderings (i.e., SPT-I → SPT-T or SPT-T → SPT-I). We aimed to have a balance of aphasia severity and AOS severity reflected in the treatment orders. The first participant enrolled was randomly assigned to a treatment condition. Each subsequently enrolled participant was “matched” to a previously enrolled participant and assigned to the opposite group if he/she had the same aphasia type, had an AQ within 10 points of the match, and had the same AOS severity rating. When a match did not exist, then the participant was randomly assigned to a treatment order. Please note that the purpose of the investigation was not to compare performance relative to treatment order as all participants received both treatments. The matching and random assignment was conducted to minimize possible confounds associated with treatment order.

As indicated previously, each participant received both SPT-T and SPT-I. Two sets of experimental words were devised for each participant (described below). Those sets were randomly assigned to treatment condition to assist in controlling for influence of stimuli on treatment outcome.

Experimental Stimuli and Probe Procedures

Stimuli. As indicated, two sets of words were individually developed for each participant. For each set, there were three subsets, each of which represented a different sound target.

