Pretreatment assessment of word production was used to identify specific sounds that were difficult for the participant to produce. There were a total of 39 words per set, with 24 items designated for treatment and 15 items designated for generalization measurement. Across the participants, stimuli included monosyllabic words, multisyllabic words, and words in phrases.

Probes. Production of the experimental words was elicited in probes. During probes the examiner presented each word verbally, one at a time in random order, and asked the participant to repeat the word as accurately as possible. No feedback concerning accuracy of production was provided; only general encouragers (e.g., you're trying hard) were used. The treatment items were included in probes to measure the *acquisition effects* of treatment and the untreated exemplars of trained items were used to measure the *response generalization* effects of treatment (see Dependent Variable). All probe sessions were audio recorded.

Probes were conducted throughout all phases of the study. Prior to all treatment, three separate probes were completed with all stimuli. During each treatment phase, six probes were conducted. During the two-week no-treatment interval, the "to be treated" set was probed an additional three times to establish a second baseline before the second treatment. Follow-up probes were completed at 2 and 8 weeks post each treatment phase.

Dependent Variable

The dependent variable was accuracy of articulation of a target sound or sounds produced in words elicited in the probes. A single score of correct or incorrect was used for each experimental item. Scoring was completed using on-line, modified narrow transcriptions supplemented and verified with audio recordings. The target sound(s) for each experimental word was/were identified and determined to be accurately or inaccurately produced on the basis of the transcription. Then, the word containing the target sound(s) was given a score of “correct/incorrect”. For each subset of items for each participant, the percentage of words in which the target sounds(s) was produced correctly was tallied from the verified, online productions; the subsets were further separated into trained and untrained subsets. These percentages served as the dependent variables for all analyses.

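### Intense and Traditional are compared only on d, never on percentage-point gain; the Table 2 Intense row is impossible as printed, and d cannot be reproduced as described

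*SAP*

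**What the plan says.** The protocol (Dependent Variable) scores each word correct or incorrect. It tallies percentages correct by subset, split into trained and untrained items, and adds: "These percentages served as the dependent variables for all analyses". Under Experimental Stimuli, each set has three subsets, and "There were a total of 39 words per set, with 24 items designated for treatment and 15 items designated for generalization measurement". Under Probes, the set awaiting the second phase "set was probed an additional three times to establish a second baseline before the second treatment", so both phases have three probes just before treatment.

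The SAP (Effect Sizes) then forms one d per participant, condition and item type: follow-up value minus baseline mean, divided by the baseline SD. For the data used, "the three baseline probes immediately preceding application of treatment were used along with the probe completed at two weeks post-treatment". The intensity question is tested only on these values: "Comparisons of average group effect sizes were completed using parametric statistics" (dependent t-tests, or a signed-rank test if normality fails). Treated items give t(23) = 2.698, p = .0128; untreated items give t(23) = .0735, p = .942. The conclusion for treated items is that "the 2 week follow-up effect size sample mean for Traditional intensity treatment exceeded that for the Intense treatment".

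Table 1 (treated): Intense mean 19.7, SD 12.6, range 5.2 to 49.1; Traditional 28.9, 17.2, 6.5 to 53.1. Table 2: Intense 7.9, 5.6, -4.1 to 34.6; Traditional 8.1, 8.9, -1.0 to 20.9. Table 2 is captioned as treated items, but the SAP text assigns its means to untreated items.

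**The concern.** An SD from three probes has 2 degrees of freedom. Dividing by it makes d depend heavily on how steady three pre-treatment scores happened to be. A difference in mean d between conditions may reflect gain, baseline scatter or both, and the reported test cannot separate them. Intensity is the trial's comparison of interest, and percentages are its declared dependent variable, yet no between-condition contrast of percentage-point gain appears. A reader who wants to know whether one schedule led to more words produced correctly has no figure to use.

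The second issue is whether the tabled d-values can be reproduced. One row of Table 2 does not fit together, and two maxima look too large for the formula as most readers would apply it. If individual d-values are wrong, the means and t-tests built on them are affected. If only a printed summary figure is wrong, the tests are untouched. The documents do not show which is the case.

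**Working it through.** **1. The plan's own tests.** With 23 degrees of freedom, t = 2.698 gives p = .0128 and t = .0735 gives p = .942. Both reproduce.

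**2. Size of the differences (d-units).** The critical t(23) is 2.0687.
- Treated: 28.9 - 19.7 = 9.2; SE = 9.2/2.698 = 3.4099; margin 2.0687 × 3.4099 = 7.054; 95% CI 2.1 to 16.3.
- Untreated: 8.1 - 7.9 = 0.2; SE = 0.2/.0735 = 2.721; margin 5.629; 95% CI about -5.4 to 5.8. The means are rounded, so this is approximate. The SD of a paired difference cannot exceed the sum of the two SDs, 5.6 + 8.9 = 14.5 (14.6 allowing for rounding). The SE is then at most 14.6/√24 = 2.980. With t = .0735 the difference is 0.219 and the widest interval is about -5.9 to 6.4.

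**3. What d measures.** Take 20 of 24 treated items correct at follow-up (illustrative scores) and an n-1 SD.
- Baseline 0, 0, 1: gain 20 - 0.333 = 19.7 items; SD 0.577; d = 34.1.
- Baseline 0, 0, 2: gain 20 - 0.667 = 19.3 items; SD 1.155; d = 16.7.

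One extra item correct on one baseline probe halves d while the gain barely moves.

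**4. Table 2, Intense row.** Inputs: n = 24, mean 7.9, minimum -4.1, maximum 34.6. The SD is smallest when the other 22 values are equal, at (24 × 7.9 + 4.1 - 34.6)/22 = 7.232.
- Sum of squares: (-12.0)² + 26.7² + 22 × (7.232 - 7.9)² = 144.00 + 712.89 + 9.82 = 866.71.
- Smallest SD: √(866.71/23) = 6.14; with divisor n, √(866.71/24) = 6.01. With divisor n and every input rounded in the most favourable direction it is 5.99.
- Printed: 5.6. The row cannot hold.

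The same bounds applied to two possible misprints:

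| Swap within Table 2 | Intense: SD, feasible range | Traditional: SD, feasible range |
|---|---|---|
| The two SDs | 8.9, 6.1 to 18.3 | 5.6, 3.3 to 11.0 |
| The two maxima | 5.6, 3.7 to 12.8 | 8.9, 5.9 to 15.9 |

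Either swap makes both rows possible.

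**5. Largest d on whole-set scores.** Assume exact percentages, three probes and a non-zero SD. The largest d comes from baseline 0, 0, 1 and a perfect follow-up. The baseline SD in items is √(1/3) = 0.577 (n-1) or √(2/9) = 0.471 (n).
- 24 items: 23.667/0.577 = 41.0, or 23.667/0.471 = 50.2. Tabled maximum 53.1.
- 15 items: 14.667/0.577 = 25.4, or 14.667/0.471 = 31.1. Tabled maximum 34.6.

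Neither maximum is reached. The Table 1 Intense maximum of 49.1 is above the n-1 ceiling but below the n ceiling.

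**6. Other readings.** The protocol tallies percentages by subset, so d might be computed on the average of three subset percentages. Subset sizes are not given; those below are assumed, with an n-1 SD.
- Treated 8/8/8, each percentage rounded to a whole number: set averages of 8.33, 8.33, 8.67 are possible at baseline, and the ceiling is about 476.
- Untreated 4/5/6, exact percentages: ceiling about 270.
- Untreated 5/5/5, exact percentages: ceiling stays at 25.4.

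Some three-probe readings therefore do allow 53.1 and 34.6. A substituted SD when all three baseline scores are equal could do so too; d is undefined in that case and the SAP gives no rule.

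**The case against.** The strongest reply has three parts.

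First, d is a defined metric, it links to the published benchmarks the SAP cites, and the SAP words its conclusion in effect-size terms. Nothing in the documents shows that baseline scatter differed between conditions, and word sets were allocated at random: "Those sets were randomly assigned to treatment condition to assist in controlling for influence of stimuli on treatment outcome". All of this stands. A reader might infer that the treated-item result is biased or an artefact of the denominator. The documents do not support that, and the example in step 3 is hypothetical. What remains is that the percentages, the declared outcome, are never contrasted between conditions.

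Second, a reader might infer that 53.1 and 34.6 are impossible under the stated formula. That is too strong. It holds for exact whole-set scoring only, and the protocol's subset tally leaves room for averages that go far higher. Unstated subset sizes cannot be held against the figures; the missing description can.

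Third, the Table 2 conflict may be a simple misprint that leaves the t-tests untouched. That is plausible, as the swaps show, but a misprint also needs correcting. The caption conflict does not remove it: the row fails on its own four figures and n = 24, whichever item type it describes. If the caption were right and the table showed treated items, 34.6 would lie below 41.0, but the SD would still be impossible.

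**Conclusion.** The point stands in three parts of different strength.

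- **Certain:** the Table 2 Intense SD of 5.6 cannot accompany the other figures in its row; at least 6.1 is needed, or 5.99 on the most lenient reading. This rests only on n = 24 and the printed row. The table's caption also contradicts the text.
- **Clear from the text:** intensity is tested only on d, whose denominator has 2 degrees of freedom. The treated difference of 9.2 d-units (95% CI 2.1 to 16.3) and the untreated difference of about 0.2 (95% CI about -5.4 to 5.8, at most about -5.9 to 6.4) have no equivalent in words. The wider limit relies on the Table 2 SDs; either swap leaves their sum, and so the limit, unchanged. Whether p = .0128 would persist on percentage points cannot be judged from the documents.
- **Conditional:** 53.1 and 34.6 exceed the ceilings if d uses exact whole-set scores from three probes. This shows only that the calculation is not reproducible as described, not that the values are wrong.

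This should be fixed. It does not overturn the reported tests.

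**What to change.** 1. Check the Table 2 Intense row and the table's caption against source data and correct them.
2. Check 53.1 and 34.6 against source data. State in the SAP the scoring unit (whole set or average of subsets), the SD divisor, the rounding of percentages and any handling of a zero baseline SD. Re-run the t-tests if any d-value changes.
3. Add a paired Intense versus Traditional comparison of percentage-point change (2-week follow-up minus the mean of the three baseline probes), separately for treated and untreated items, with mean difference and 95% CI. Label it post hoc supplementary and show it beside the d test.
4. Keep d for the benchmark comparison and limit conclusions from d to the d scale.

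Cost: SAP wording, a short source-data check and one additional analysis on data already held. Downsides: the added contrast is post hoc, is not in benchmark units, and is limited by floor and ceiling effects on a percentage scale.

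### The two-period cross-over is tested without a period term, and nothing reported by treatment order lets a reader check that this is harmless (minor)

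*SAP*

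**What the plan says.** The SAP (Effect Sizes) names two arms, Intense First and Traditional First, and says: "The arms reflect counterbalancing of order of treatment administration". It treats order as not of interest because "there is no evidence to suggest that treatment order would be a pertinent factor in treatment response". It then pools over order: "the data from the Intense phase of treatment for all 24 participants was analyzed relative to the data from the Traditional phase". The test, described after Table 2, is a two-tailed dependent t-test, with the Wilcoxon signed rank test as fallback. The treated-item result is t(23) = 2.698, p = .0128. Tables 1 and 2 are by condition only.

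Each d is standardised by its own baseline: "the three baseline probes immediately preceding application of treatment were used along with the probe completed at two weeks post-treatment". For the second phase, that baseline is the extra set of three probes taken in the interval after the first treatment course (Protocol, Probes).

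The Protocol (Treatment Order and Experimental Set Assignment) sends a participant who matches an earlier one to the opposite order. Otherwise: "When a match did not exist, then the participant was randomly assigned to a treatment order". No block or cap is stated. The stated aim is precautionary: "The matching and random assignment was conducted to minimize possible confounds associated with treatment order". There are further safeguards. On the word sets: "Those sets were randomly assigned to treatment condition to assist in controlling for influence of stimuli on treatment outcome". A two-week "no-treatment interval followed the first treatment phase", and stability of the second set was checked before it was treated.

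**The concern.** In a two-period cross-over, period is a nuisance factor in the treatment comparison whether or not anyone is interested in order. Declaring order uninteresting does not remove it from the paired difference. What happens depends on the arm sizes:

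- **Equal arms:** an additive period effect cancels from the mean difference but stays in the error term.
- **Unequal arms:** it also biases the mean difference.

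The two documents do not show which case applies, and the sentence offered in place of data cannot be checked.

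A period effect is plausible on this particular scale. The second-phase d divides by the SD of three probes taken after a full course of the first treatment. A systematically different baseline mean or SD at that point would shift d even if the raw gain were the same. Random assignment of word sets, the interval and the stability check help, but none of them makes the baseline SD equal in the two periods or fixes the arm sizes.

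The result at stake is the treated-item difference, the only significant group comparison reported.

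**Working it through.** **Inputs (SAP Table 1 and the paragraph after Table 2).** Treated-item means are 28.9 (Traditional) and 19.7 (Intense), with n = 24 and t(23) = 2.698. Arm sizes and the period effect are not given and are assumed below. Neither document states alpha; .05 is assumed.

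**Reproducing the plan's figure.**
- Difference = 28.9 − 19.7 = 9.2
- SE = 9.2/2.698 = 3.41
- SD of differences = 3.41 × √24 = 16.7
- Two-tailed p on 23 df = .0128, as stated; 95% CI 2.1 to 16.3

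The 23 df confirm that no period term was fitted; with one there would be 22.

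**Period-adjusted estimate.** Let δ be the additive period effect (period 2 minus period 1), and nIF and nTF the numbers with Intense First and Traditional First.
- Bias of the paired difference = δ × (nIF − nTF)/24
- Adjusted difference = 9.2 − bias
- Residual SS = 23 × 16.7² − (2δ)² × nIF × nTF/24
- SE = 0.5 × √(residual SS/22) × √(1/nIF + 1/nTF), with t on 22 df

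**Size of δ (illustrative).** The values are 0.15, 0.32 and 0.5 of 16.7, that is 2.5, 5.3 and 8.4 d-units. For scale, the overall mean d is (28.9 + 19.7)/2 = 24.3. If the raw gain is unchanged and the second-phase baseline SD is r times the first, the period difference is 2 × 24.3 × (1 − r)/(1 + r). That gives 2.6, 5.4 and 8.2 for r = 0.9, 0.8 and 0.71. Nothing in the documents supports a size or a direction.

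**Treated items, adverse direction** (effect favours period 2 and Intense First is the larger arm, or the mirror case). Cells show adjusted difference and p:

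| Split | δ = 0 | 0.15 SD | 0.32 SD | 0.5 SD |
|---|---|---|---|---|
| 12/12 | 9.2, .015 | 9.2, .014 | 9.2, .011 | 9.2, .006 |
| 14/10 | 9.2, .016 | 8.8, .020 | 8.3, .021 | 7.8, .018 |
| 16/8 | 9.2, .021 | 8.4, .032 | 7.4, .047 | 6.4, .060 |

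For example, at 16/8 and 0.5 SD the bias is 8.35 × 8/24 = 2.8, so the difference is 9.2 − 2.8 = 6.4 (95% CI −0.3 to 13.1). In the other direction p falls: .012, .005 and .001 at 16/8.

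**Tipping point.** Over effects from 0 to 1 SD in either direction (as far as the reported SD allows), the maximum p is .015 at 12/12, .021 at 14/10 and .033 at 15/9. At 16/8, p exceeds .05 for adverse effects of 0.36 to 0.84 SD; at 17/7, from 0.20 SD.

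**Precision with equal arms.** The adjusted SE is 3.45, 3.30 and 3.00 for the three effects, against 3.41 paired. It is smaller only when (23 − 24k²)/528 < 1/24, where k is the effect in SD units, that is k above 0.204 or about 3.4 d-units.

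**Type I error of the paired test** (nominal 5%, normal differences, 200,000 simulated trials per cell): about 5%, 4% and 2.5% at 12/12, and about 5%, 7% and 9% at 16/8.

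**Untreated items.** With the difference taken as 0.2 (8.1 − 7.9), the adjusted p stays at .36 or above for splits up to 16/8 and is .28 at lowest at 17/7, for effects up to 0.5 SD.

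**The case against.** No error in the result is shown. A paired comparison in a counterbalanced cross-over is a recognised analysis, and with equal arms an additive period effect makes it conservative. Every scenario that changes the conclusion needs a 16/8 or worse split, a sizeable period effect and the adverse direction, all together. Under pure coin-toss allocation, 16/8 or worse has probability 15% and 17/7 or worse 6.4%, with half of each in the adverse direction; matching should lower these. All of this stands and is why the point is minor. The number of matched participants is not given, so the true probability cannot be stated.

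The mechanism offered (a changed baseline SD) multiplies d, whereas the grid and the adjustment assume an additive effect with common variance. This is correct. If T and I are the Traditional and Intense means at the first-phase baseline SD, the two orders' differences would be T/r − I and T − I/r. The variances could differ, and the equal-weight mean would be (T − I)(1 + 1/r)/2. The p-values above are therefore approximate for that mechanism.

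The disputed sentence can be read as a statement of prior knowledge, and 24 participants cannot establish that order has no effect. That is fair. By-order data would still let a reader see the arm sizes and the observed pattern. The Protocol's aim of limiting order confounding is a design precaution and does not contradict the SAP.

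**Conclusion.** The concern holds as a minor point. The analysis omits a period term, its justification is asserted without data, and neither document gives counts or means by order. Neither document shows a period effect or unequal arms, and the reported treated-item result is not shown to be wrong.

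Under an additive effect of at most 1 SD of the differences, the treated-item conclusion survives every split up to 15/9. It is lost only at about 16/8 or worse with an effect of at least 0.36 SD (0.20 SD at 17/7) in the adverse direction. The untreated-item conclusion does not change in any case tried. These statements rest on assumed arm sizes and effects, on the rounded published means and t-values, and on an assumed .05 level.

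**What to change.** Four changes to the SAP and its results:

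1. Report n and mean d by order and period, for treated and untreated items.
2. Add a period-adjusted intensity estimate with 95% CI: the equal-weight mean of the two orders' within-person differences, which is the intercept when the difference is regressed on order coded ±1 (22 df). Label it as added after the results were known.
3. Support the no-evidence sentence with the by-order data, or delete it.
4. State that a period term does not remove differential carry-over from the first treatment to the second.

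The cost is wording and one rerun on data already held. If there is no period effect, the analysis loses one degree of freedom and the interval widens slightly, from 2.1 to 16.3 to 2.0 to 16.4 at 12/12 or 1.5 to 16.9 at 16/8. The treated-item p then moves from .013 to .015 or .021.

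### SAP Table 2, Intense row: an SD of 5.6 is impossible for 24 values with mean 7.9, minimum -4.1 and maximum 34.6; the SD must be at least about 6.0

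*SAP*

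**What the plan says.** The SAP (Effect Sizes) computes d-values for each participant and condition and summarises them in two tables. In Table 2 the Intense row reads "7.9 5.6 -4.1 34.6" and the Traditional row "8.1 8.9 -1.0 20.9", in the order mean, SD, minimum, maximum. The caption describes the table as "Descriptive Statistics for Treated Items by Treatment Condition for the Group of 24 Participants". That is also Table 1's caption, yet the Table 2 means are those the text gives for untreated items, where large effects "were found for both SPT-Traditional (d=8.1) and SPT-Intense (d=7.9".

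The text directs the reader to the extremes for the variation between people: "As reflected by the minimum and maximum values in Tables 1 and 2, there were wide ranges of effect sizes found across the individuals". For untreated items the SAP reports a dependent t-test, t(23) = .0735, p = .942, and concludes that "there was not a statistically significant difference between treatment intensity conditions". The choice of test depended on the data: a t-test where possible, and "the nonparametric analogs when normality tests were failed".

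**The concern.** A maximum of 34.6 lies 26.7 above a mean of 7.9. With only 24 values, that one participant contributes so much to the sum of squares that an SD of 5.6 looks too small, even before the minimum is counted.

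The row describes one side of the untreated-item (response generalization) comparison, and Table 2 is the only place where the spread of those effects is given. A reader who takes the Intense SD into a pooled analysis or a sample-size calculation would be using an impossible value. If two figures were exchanged between rows, the spread is attached to the wrong condition. If instead a d-value in the analysis file is wrong, the normality check and the test that depended on it are affected too.

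**Working it through.** **Inputs.** n = 24 (Table 2 caption; SAP text; 23 df in the test). Mean 7.9 (Table 2, repeated in the text). SD 5.6, minimum -4.1, maximum 34.6 (Table 2).

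**Smallest possible SD.** With the mean and both extremes fixed, the sum of squares is least when the other 22 values are all equal.

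- Common value: (24 × 7.9 + 4.1 - 34.6)/22 = 7.232, which is 0.668 below the mean.
- SS = 12.0² + 26.7² + 22 × 0.668² = 144.00 + 712.89 + 9.82 = 866.71.
- Divisor n-1: √(866.71/23) = 6.14. Divisor n: √(866.71/24) = 6.01.
- Moving the mean, minimum and maximum by up to 0.05 in the most favourable direction: 6.12 and 5.99.

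The printed 5.6 is at most 5.65 before rounding, below every variant. Even with divisor n and favourable rounding, at least 27 values would be needed.

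**The same test on the other rows (divisor n-1).**

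| Row | Smallest SD | Printed SD | Largest SD |
|---|---|---|---|
| Table 1 Intense | 6.87 | 12.6 | 21.1 |
| Table 1 Traditional | 6.88 | 17.2 | 23.8 |
| Table 2 Intense | 6.14 | 5.6 | 18.3 |
| Table 2 Traditional | 3.28 | 8.9 | 11.0 |

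Only the Table 2 Intense row fails.

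**Which single figure could be wrong, with divisor n-1.**

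- Mean alone: no. The range by itself forces an SD of at least 38.7/√46 = 5.71 (38.6/√46 = 5.69 with rounding), above 5.65.
- Minimum alone: no, though narrowly. The maximum lies (34.6 - 7.9)/5.6 = 4.77 SDs above the mean, or (34.55 - 7.95)/5.65 = 4.71 with rounding. The most that 24 values allow is 23/√24 = 4.69.
- Maximum alone: yes. With mean 7.9, minimum -4.1 and SD 5.65, the maximum can be at most 32.1.
- SD alone: yes, if it is at least 6.14 (6.12 with rounding).

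**With divisor n** (the SAP does not state which was used), the maximum could be at most 32.7. A repair by the mean alone would need at least 12.1, against the 7.9 that the text repeats. A repair by the minimum alone would need at least 1.6 instead of -4.1.

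**Exchange between the Table 2 rows (divisor n-1).**

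- SDs exchanged: Intense needs 6.14 and would have 8.9; Traditional needs 3.28 and would have 5.6.
- Maxima exchanged: Intense needs 3.69 and has 5.6; Traditional needs 5.89 and has 8.9.

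All four are feasible.

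**Tests.** On 23 df, t = 2.698 gives p = .0128 and t = .0735 gives p = .942, as reported. For treated items the implied SD of differences is 9.2 × √24/2.698 = 16.7, and the implied correlation is (12.6² + 17.2² - 16.7²)/(2 × 12.6 × 17.2) = 0.40, which is plausible. For untreated items the rounded means allow a difference of 0.1 to 0.3. The implied SD of differences then starts at 0.1 × √24/.0735 = 6.7. If the two printed SDs are right, exchanged or not, it is capped at their sum, 5.65 + 8.95 = 14.6 with rounding. If the Intense SD alone is wrong, that cap falls away and the means alone allow up to 0.3 × √24/.0735 = 20.0. Either way the t-test cannot show which figure is at fault.

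**The case against.** The strongest objection is that the bound requires all four figures to describe the same 24 values. The Protocol (Dependent Variable) says that "For each subset of items for each participant, the percentage of words in which the target sounds(s) was produced correctly was tallied", and each set has three subsets. If d was computed per subset, the extremes could come from up to 72 subset values while the mean and SD were taken over 24 participant averages; the printed figures could then coexist. If all four figures described 72 values, the smallest SD would fall to √((144.00 + 712.89 + 14.7²/70)/71) = 3.48. But the caption refers to the group of 24 participants, and the text presents the extremes as variation between individuals. On that reading the table would be mislabelled, so it would still need correction.

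Two cautions stand. Narrowing a single error to the SD or the maximum depends on divisor n-1, and the exclusion of the minimum is close (4.71 against 4.69). The practical reach is also limited: one descriptive row on a comparison that was not significant. A misread digit in the PDF cannot be strictly excluded, but it is unlikely, since the four figures stand together on one line and the mean agrees with the text.

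**Conclusion.** The concern holds. As labelled, the Table 2 Intense row is arithmetically impossible: SD 5.6 against a minimum of 6.14 (n-1), 6.01 (n) or 5.99 (most favourable rounding). The result needs no assumption about the distribution of d or the formula behind it, only that the four figures summarise the same 24 values, as the caption and text say. At least one of them is wrong. If only one is, and the divisor is n-1, it is the SD or the maximum. An exchange between rows is a live explanation, and the repeated caption fits a copying slip without proving one.

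No conclusion is shown to be wrong. An exchange of SDs or maxima would leave unchanged the means, the large-effect statement (7.9 against the benchmark of 6.47) and both tests. The reported spread of untreated-item effects should not be used until it is corrected.

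**What to change.** Check both Table 2 rows against the 24 individual d-values per condition, correct whichever figure or figures are wrong, and change the caption to untreated items. If any d-value used in the analysis proves wrong, repeat the normality check and the untreated-item comparison. Extend the check to Table 1 and the treated-item comparison only if the error lies in how d was computed.

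As a minor reporting addition, not an error, state how subset percentages were combined into one d per participant, which SD divisor was used, and how a zero baseline SD was handled; the documents give none of these.

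The cost is a check of 48 existing values and a corrected table. No new data are needed.
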